5.2.3. Secondary Efficacy Endpoints

The secondary efficacy endpoints for the study are as follows:

- 1. Change from baseline to Day 15 and Day 29 in the SPEED questionnaire total symptom score.
- 2. Changes from baseline to Day 15 and Day 29 in each of the 7-item symptom questionnaire scores.
- 3. Change from baseline to Day 15 and Day 29 in staining of the Lid Wiper area.
- 4. Change from baseline to Day 15 and Day 29 in bulbar conjunctival staining total score.
- 5. Change from baseline to Day 15 and Day 29 in corneal staining total score.
- 6. Changes from baseline to Day 15 and Day 29 in tear breakup time (TBUT).
- 7. Change in symptom frequency score and severity score as recorded by the subject using the SANDE Part 2 assessment.
- 8. Change from baseline to Day 15 and Day 29 in the SANDE symptom frequency and

CONFIDENTIAL Page 16 08 August 2017

- severity scores from Part 1.
- 9. The proportion of subjects with at least a 20% improvement from baseline to Day 15 and Day 29 in the SANDE global symptom score from Part 1 (and in the frequency and severity scores).
- 10. The proportion of subjects with at least a 10% improvement over 14 days from Day 1 to Day 15 and from Day 15 to Day 29 in symptom frequency score and severity score using the SANDE Part 2 assessment.

5.2.4. Secondary Efficacy Analyses

1. The SPEED questionnaire total symptom score is calculated by summing responses from the frequency of symptoms (0-3 scale) and severity of symptoms (0-4 scale) sections. There are 5 symptoms, so the total score can range from 0 to 35. The change from baseline to Day 29 in the SPEED questionnaire total symptom score will be analyzed in a similar manner as the primary endpoint. A secondary analysis will be performed assessing the change from baseline at Day 15.

Additionally, the proportion of subjects with improvement from baseline, no change from baseline, and worsening from baseline to Day 29 will be summarized by treatment group and overall. The analysis will be repeated at Day 15.

The descriptive statistics for change from screening to baseline will be presented.

The type of symptoms and when they occur from question 1 on the SPEED questionnaire will be summarized by treatment at Day 15 and Day 29.

Mean and 95% CI for SPEED questionnaire total symptom scores will be plotted by treatment and study visit.

2. The 7-item questionnaire comprises 100mm VAS scales for 7 symptoms: Eye dryness, Burning/Stinging, Photophobia, Foreign Body Sensation, Blurred Vision, Itching, and Pain. The scales range from no discomfort (0) to maximal discomfort (100). Changes from baseline to Day 29 in each of the 7 measurements will be analyzed individually in a similar manner as the primary endpoint. A secondary analysis will be performed assessing the change from baseline at Day 15.

Additionally, the proportion of subjects with improvement from baseline, no change from baseline, and worsening from baseline to Day 29 will be summarized by treatment group and overall. The analysis will be repeated at Day 15.

The descriptive statistics for change from screening to baseline will be presented by treatment.

CONFIDENTIAL Page 17 08 August 2017

Mean measurements and 95% CI for these questionnaires will be plotted by treatment and study visit separately for all 7 items.

Lid wiper staining is measured using a horizontal length of staining score (0-3) and a sagittal height of staining score (0-3). The individual scores for these two dimensions are averaged to calculate a final Fluorescein staining score and Lissamine Green staining score. The staining score of the lid wiper area is defined as the maximum of the Fluorescein and Lissamine scores. Thus, possible values for the staining score of the lid wiper area are: 0, 0.5, 1, 1.5, 2, 2.5, and 3. The primary analysis for the change from baseline to Day 29 will utilize the Study Eye and will be analyzed in a similar manner as the primary endpoint. An additional analysis will be conducted using scores from all qualifying eyes. For this analysis, the change from baseline at Day 29 will be assessed using a mixed model repeated measures analysis with fixed effects for treatment, study site, visit, eye, and treatment by visit interaction with the baseline value as a covariate and a random effect for subject. The following 3 covariance structures will be considered: AR(1), CS, and UN. The covariance structure with the lowest AIC will be selected. A secondary analysis will be performed assessing the change from baseline at Day 15 from the same mixed model.

The descriptive statistics for change from screening to baseline will be presented by treatment.

The analysis will be repeated for Fluorescein scores and Lissamine scores independently.

Mean and 95% CI for staining scores of the lid wiper area will be plotted by treatment and study visit.

4. Bulbar conjunctival staining total score is defined as the sum of scores from 6 regions: Temporal, Temporal Superior, Temporal Inferior, Nasal Superior, Nasal Inferior, and Nasal. The score for each region ranges from 0 to 3. Thus, the bulbar conjunctival staining total score can range from 0 to 18. The change from baseline to Day 29 will be analyzed in a similar manner as the Change from baseline to Day 29 in staining of the Lid Wiper area. A secondary analysis will be performed assessing the change from baseline at Day 15.

The descriptive statistics for change from screening to baseline will be presented by treatment.

The analysis will be repeated for the inferior nasal region (region 5) individually.

Mean and 95% CI for bulbar conjunctival staining total scores will be plotted by treatment and study visit.

5. Corneal staining total score is defined as the sum of scores from 5 regions: Central, Superior, Temporal, Nasal, and Inferior. The score for each region ranges from 0 to 3. Thus, the corneal staining total score can range from 0 to 15. The change from baseline to Day 29 will be analyzed in a similar manner as the Change from baseline to Day 29 in staining of the Lid Wiper area. A secondary analysis will be performed assessing the change from baseline at Day 15.

CONFIDENTIAL Page 18 08 August 2017

The descriptive statistics for change from screening to baseline will be presented by treatment.

The analysis will be repeated for the inferior region (region 5) individually.

Mean and 95% CI for corneal staining total scores will be plotted by treatment and study visit.

6. The change from baseline to Day 29 in TBUT (seconds) will be analyzed in a similar manner as the Change from baseline to Day 29 in staining of the Lid Wiper area. A secondary analysis will be performed assessing the change from baseline at Day 15.

The descriptive statistics for change from screening to baseline will be presented by treatment.

Mean and 95% CI of TBUT will be plotted by treatment and study visit.

7. The SANDE Part 2 is comprised of two 100mm VAS scales. One measures the frequency of symptoms at the current visit as compared to the frequency of symptoms at the previous visit. The score ranges from much less frequent (-50) to much more frequent (50). The second VAS measures the severity of symptoms at the current visit as compared to the severity of symptoms at the previous visit. The score ranges from much less severe (-50) to much more severe (50).

The change from previous visit for frequency and severity of symptoms will be summarized individually by treatment at Day 1, Day 15, and Day 29. Differences between the 0.017% P-321 treatment group and placebo will be assessed using a mixed model repeated measures analysis with fixed effects for treatment and study site, visit, and visit by treatment interaction. The following 3 covariance structures will be considered: AR(1), CS, and UN. The covariance structure with the lowest AIC will be selected.

Additionally, the proportion of subjects with improvement from previous visit, no change from previous visit, and worsening from previous visit at Day 1, Day 15, and Day 29 will be summarized by treatment group and overall.

8. The SANDE Part 1 is comprised of two 100mm VAS scales. One measures frequency of symptoms from rarely (0) to all the time (100). The other measures severity of symptoms from very mild (0) to very severe (100). The change from baseline to Day 29 in the SANDE symptom frequency and severity scores from Part 1 will be analyzed individually in a similar manner as the primary endpoint. A secondary analysis will be performed assessing the change from baseline at Day 15.

Additionally, the proportion of subjects with improvement from baseline, no change from baseline, and worsening from baseline to Day 29 will be summarized by treatment group and overall. The analysis will be repeated at Day 15

CONFIDENTIAL Page 19 08 August 2017

- 9. Subjects whose SANDE global symptom score from Part 1 decreases by 20% or more from baseline to Day 29 will be considered responders. Subjects whose scores do not decrease by 20% or more will be considered non-responders. Differences between the proportion of responders between the 0.017% P-321 treatment group and placebo will be assessed using a logistic regression model with fixed effects for treatment, study site, and baseline value. The odds ratio and corresponding 95% confidence interval will be presented. The analysis will also be performed for the frequency and severity scores individually. A secondary analysis will be performed assessing the change from baseline at Day 15.
 - A Sensitivity analysis will be performed where all subjects with missing data will be considered non-responders.
- 10. A 10% or more improvement from previous visit will be defined as a SANDE Part 2 value of 5 or more. Subjects whose scores show an improvement of symptoms by 10% or more from baseline to Day 15 will be considered responders at Day 15. Subjects whose scores show an improvement of symptoms by 10% or more from Day 15 to Day 29 will be considered responders at Day 29. Differences between the proportion of responders between the 0.017% P-321 treatment group and placebo will be assessed separately at Day 15 and at Day 29 using a logistic regression model with fixed effects for treatment and study site.

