1 PROTOCOL SYNOPSIS

Name of Sponsor:		Study Medication:
Parion Sciences, Inc.		0.017% P-321 Ophthalmic Solution
Protocol Number:	Phase:	Indication:
P-321-202	2b	Treatment of dry eye disease
Title of the Study:	•	·

Title of the Study:

Randomized, Double-Masked, Parallel Group Study of P-321 Ophthalmic Solution Compared to Placebo in Subjects with Dry Eye Disease Assessing Safety and Efficacy Over 28 Days

Study Center:

Approximately 7 centers in the United States

Study period (FPFV - LPLV): Approximately 6 months

Anticipated first subject enrolled: 4Q2016

Anticipated last subject complete: TBD

Objectives:

[figure not shown]
Primary objective

To evaluate the effect of treatment with 0.017% P-321 on Dry Eye Symptoms

Secondary objective

- To assess changes in conjunctival staining of the Lid Wiper area
- To assess changes in corneal staining
- To assess changes on the bulbar conjunctival staining
- To assess changes in TBUT
- To monitor safety and tolerability of P-321 Ophthalmic Solution through adverse events, biomicroscopy and external eye examination, and other safety assessments

Exploratory objectives include expression of biomarkers in the bulbar conjunctiva, lid wiper, and in tears.

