
Number of Subjects Randomized:	Number of Centers:
Approximately 65 randomized to complete 60 subjects	Approximately 7
Test Product and Doses:	Route of Administration:
0.017% P-321 Ophthalmic Solution	Ocular instillation, one drop per eye TID for 28 days
Reference Product and Doses:	Route of Administration:
Placebo (vehicle)	Ocular instillation, one drop per eye TID for 14 days in the run-in period and for 28 days in the double-masked treatment period

Duration of Treatment:

Eligible subjects will receive placebo TID in both eyes from Visit 1 and through the evening before Visit 2 (for 14 days). Starting at Visit 2 (Randomization – Treatment Day 1) and continuing through the day before Visit 4, subjects will receive 0.017% P-321 Ophthalmic Solution or Placebo TID in both eyes. A follow up call will be scheduled 5-9 days after the Visit 4. Total duration of the study is expected to be approximately 50 days including placebo-run-in, treatment and follow up. Three phone calls to remind subjects of dosing regimen and to inquire about adverse effects will also be done during the study and will occur between Visits 1 and 2, Visits 2 and 3, and Visits 3 and 4.

Criteria for Evaluation:

This study will evaluate the efficacy and safety of P-321 Ophthalmic Solution and Placebo in subjects with dry eye. Background characteristics will be evaluated to better characterize subjects at entry including: demographics, BCVA, dry eye symptoms upon entry, osmolarity, meibography (if available), meibomian gland evaluation, Screening IOP and Schirmer's test, medical history, and concomitant medication use.

Efficacy

Symptoms and signs will be assessed throughout the study. Symptoms will be assessed by subject-reported symptom questionnaires (SANDE and SPEED questionnaires and a 7-item symptom questionnaire). Signs will be assessed by staining of the cornea, bulbar conjunctiva, the lid wiper region of the upper eyelid and by TBUT. Exploratory assessments will include biomarkers of inflammation in tears and from impression cytology samples collected from the lid wiper and the bulbar conjunctiva.

Safety

Safety will be assessed throughout the study by adverse event monitoring, biomicroscopy and external eye examination, BCVA, physical examinations, vital signs, drop instillation comfort assessments, and clinical laboratory tests.

Statistical Analysis:

Sample Size

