11.4.3 Secondary Efficacy Analyses

The proportion of subjects with a $\geq 20\%$ improvement from baseline to Day 29 in the global symptom score from SANDE Part 1 in the 0.017% and placebo arms will be analyzed via logistic regression. The model will include all subjects in the mITT population, and subjects with a $\geq 20\%$ improvement will be considered responders. Subjects with a < 20% improvement will be considered non-responders. Responder status (yes/no) will be the dependent variable in the model, and the model will include the treatment, study site, and baseline SANDE Part 1 global symptom score as fixed effects. A significance test of the treatment difference will be tested at the two-sided 0.05 level, and odds ratios and their corresponding 95% confidence intervals will be calculated. Details regarding the handling of missing data due to early withdrawals or missed assessments will be described in the SAP. The proportion of subjects improving as evaluated using the SANDE Part 2 assessment will be analyzed in a similar manner.

Continuous secondary endpoints including the change from baseline in: the total SPEED symptom score, each of the items from the 7-item symptom questionnaire, total corneal staining score, total bulbar conjunctival staining score, lid wiper area staining score, and TBUT will be analyzed in a similar manner as the primary endpoint. The model will be changed to include the baseline value of the secondary endpoint instead of the baseline SANDE Part 1 global symptom score. Other endpoints, such as the change from baseline in the staining score of certain regions of the cornea, will be explored and analyzed in a similar manner. Further details will be provided in the SAP, along with details on how the change from baseline over the entire 28 day treatment period using the SANDE Part 2 assessment and the definition of improvement over 28 days using the SANDE Part 2 assessment will be defined.

The primary evaluation of interest for secondary endpoints measuring signs of dry eye will utilize the Study Eye. Additional analyses will be performed for all qualifying eyes. Analyses utilizing all qualifying eyes will account for the correlation between eyes within subjects. Total conjunctival and corneal staining scores will be defined as the sum of the scores from all six and five regions, respectively. The staining score of the lid wiper area will be defined as noted in the Study Manual.

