3.1. SAMPLE SIZE AND POWER

A sample size of approximately 65 randomized subjects is proposed. Assuming a dropout rate prior to Visit 3 of 10%, this provides approximately 60 subjects with post-baseline data. The sample size estimation was based on assumptions about the standard deviation and treatment effect for the change from baseline SANDE global score (Part 2 assessment) from a previous study, protocol P-321-101. At Day 28, the pooled standard deviation for the change from baseline was 22 and the difference in means was 20, representing a standard effect size of 0.9. If the true standard deviation is 22, a sample size of 30 subjects per group will provide at least 90% power to detect a true difference in means of 20 using a two-sided hypothesis test with Type 1 error of 5%. All else being equal, this sample size provides at least 70% power if the treatment difference is at least 15 units or if the standard deviation is no more than 29.

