3.2. RANDOMIZATION AND MASKING

For the placebo run-in portion of the screening process, all subjects will receive a placebo vehicle. The placebo-run-in is single-masked in that the subjects will remain masked to treatment during the placebo run-in. However, the treatment is known to the investigator, medical monitor, study site personnel, and those involved in the conduct of the study.

Following the placebo-run-in period, approximately 65 subjects will be randomly assigned in a 1:1 allocation ratio to either 0.017% P-321 Ophthalmic Solution or placebo, stratified by clinical site. The randomized treatment assignments are double-masked in that the treatment will be masked to the investigator, medical monitor, study site personnel, subjects in the study and those involved in the conduct of the study.

CONFIDENTIAL Page 10 08 August 2017

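### If the drug works, the planned responder logistic regression overstates the odds ratio: on average by about 14-17% at a true odds ratio of 2, 25-28% at 3 and 37-42% at 4.4, with no bias at 1

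*SAP*

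**What the plan says.** SAP 5.2.4 item 9 defines a responder as a subject whose SANDE Part 1 global score falls by at least 20% from baseline to Day 29. The arms are compared with a "logistic regression model with fixed effects for treatment, study site, and baseline value". For reporting, it says: "The odds ratio and corresponding 95% confidence interval will be presented". It then extends the model to two more scores ("The analysis will also be performed for the frequency and severity scores individually") and repeats the assessment at Day 15. That makes 3 scores x 2 visits = 6 models, before the sensitivity analysis that counts missing subjects as non-responders.

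Protocol 11.4.3 agrees: "the model will include the treatment, study site, and baseline SANDE Part 1 global symptom score as fixed effects".

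The Protocol Synopsis gives the scale: "Approximately 7 centers in the United States" and "Approximately 65 randomized to complete 60 subjects". SAP 3.2 states that randomization is "stratified by clinical site", which is a good reason to keep site in the model. Neither document names a penalised, exact or conditional likelihood or a rule for pooling small sites. Neither gives an expected responder rate or odds ratio.

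**The concern.** A maximum-likelihood logistic regression is biased away from the null when there are few outcomes per parameter. Item 9 spends six parameters on site alone. Its estimated treatment odds ratio should therefore be too large on average whenever the true odds ratio differs from 1, and by more as the true effect grows.

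What is at stake is the size of the reported benefit. The odds ratio is the only model-based measure planned for the responder endpoint. It would be overstated exactly where a reader might use it, for example to judge how much benefit a later trial could expect. No false-positive claim is involved, because the bias vanishes when the drug does nothing.

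**Working it through.** **The plan's own figures.** SAP 3.1 gives power only for the continuous score. With 30 per group, a two-sided 5% t-test has about 93% power for a difference of 20 and SD 22, about 74% for 15 and SD 22, and about 75% for 20 and SD 29. These meet the stated minima of 90%, 70% and 70%. There is no stated figure for the responder analysis to reproduce.

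**Parameters.** Intercept 1 + site (7 - 1 = 6) + baseline 1 + treatment 1 = 9.

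**Outcomes per parameter.** In the simulated settings with a true odds ratio of 2 to 4.4, the smaller outcome group averaged 16 to 27 subjects: 16/9 = 1.8 to 27/9 = 3 per parameter.

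**Plausible odds ratios.** SAP 3.1 reports that "the pooled standard deviation for the change from baseline was 22 and the difference in means was 20". Let p0 be the placebo response and shift a normal score: p1 = Phi(Phi^-1(p0) + difference/22), then OR = [p1/(1 - p1)] / [p0/(1 - p0)].
- p0 = 0.30, difference 20: p1 = Phi(-0.524 + 0.909) = 0.650, so OR = (0.650/0.350)/(0.30/0.70) = 4.3.
- p0 = 0.30, difference 15: p1 = Phi(-0.524 + 0.682) = 0.562, so OR = 3.0.
- For p0 from 20% to 50%, a difference of about 9 to 9.5 gives OR 2, 15 gives 3.0-3.1 and 20 gives 4.3-4.5.

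**Simulation.** Main settings:
- 60 subjects in 7 sites, of uneven size (14, 12, 10, 8, 7, 5, 4) or even size (9, 9, 9, 9, 8, 8, 8), allocated 1:1 within site.
- Placebo response 20%, 30%, 45% or 50%, with no true site or baseline effect.
- 8,000 trials per setting (4,000 at OR 1).

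Each trial was fitted with the planned covariates, by maximum likelihood and by Firth. Inflation = exp(mean log OR estimate)/true OR - 1, with Monte Carlo 95% error of 2 to 2.5 points. Maximum-likelihood estimates with |log OR| of 6 or more (at most 35 of 8,000) were left out of the means and kept in the medians.

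| True OR | ML, geometric mean | ML, median | Bias / SD of log OR | RMSE reduction with Firth |
|---|---|---|---|---|
| 1 | -2% to +2% | - | - | - |
| 2 | +14% to +17% | +12% to +14% | 0.19-0.23 | 18-22% |
| 3 | +25% to +28% | +20% to +23% | 0.31-0.34 | 22-24% |
| 4.4 | +37% to +42% | +28% to +35% | 0.42-0.44 | 27-29% |

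In reported terms, a true odds ratio of 3 averages 3 x 1.25 = 3.75 to 3 x 1.28 = 3.84. A true 4.4 averages 4.4 x 1.37 = 6.0 to 4.4 x 1.42 = 6.2. Firth's geometric mean was 0% to +4% from the truth and its median -2% to +1%.

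**Other settings (geometric mean at OR 2, 3, 4.4).**
- 5 sites: 11-12%, 18-21%, 26-30%.
- 65 subjects in 7 sites: 15-16%, 21-24%, 32-37%.
- Real site and baseline effects: 16-17%, 27-29%, 40-42%.

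**Cross-checks.** A second simulation with 60 subjects in 7 sites varied placebo response from 20% to 60%, with equal and unequal sites and with and without site and baseline effects. It gave 14-20%, 24-33% and 39-45%, and -1% to +2% at OR 1. Simulating continuous SANDE scores and cutting them at a 20% decrease gave +43% at the design difference of 20. Without the site terms the bias fell to about 0-7%, 2-9% and 3-14%, so the site parameters cause most of it.

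**Inference under the planned model.** Type I error was 5.1-7.0% and coverage 92-95%. With Firth, type I error was 4.3-5.9% and coverage 94.1-95.8%.

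**The case against.** The strongest reply is that the plan contains no error. The protocol and SAP agree, site belongs in the model because randomization is stratified by it, and logistic regression adjusted for stratification factors is standard practice. Coverage and test level are close to nominal, the bias is well under one standard deviation of the log odds ratio, and the planned interval already shows most of the uncertainty. In one set of simulated trials with 7 sites, the maximum-likelihood estimate exceeded the truth 58-59% of the time at OR 2, 62-63% at 3 and 66-67% at 4.4, against about 50-52% with Firth. That is a tilt, not a certainty.

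The size also rests on figures that the documents do not fix. The number of sites is approximate. No responder rate is given. The difference of 20 comes from SANDE Part 2, whereas the responder endpoint uses Part 1. Protocol 3.3 says that the earlier study was not powered for efficacy. The mapping also uses one common cut-off, although a 20% decrease depends on each subject's baseline.

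All of this stands and limits the importance of the point. It does not remove the bias. The direction was the same in every setting with a true effect, and the size changed little with the assumed placebo response. Firth keeps the planned covariates and lowers both bias and RMSE, so there is no trade of bias against variance.

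**Conclusion.** The concern holds. If P-321 works, item 9 as planned will on average report too large a responder odds ratio, and by more the better the drug works. Allowing for Monte Carlo error, the geometric-mean inflation with about 60 subjects and 7 sites is about 13-20% at a true odds ratio of 2, 20-30% at 3 (one setting reached 33%) and 35-45% at 4.4. Medians run lower. Fewer sites reduce the bias, and with 65 subjects in 7 sites it was 32-37% at 4.4.

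The figures assume ordinary maximum likelihood, which is the natural reading when no other likelihood is named. They also depend on the assumed placebo response, site sizes and true odds ratios; 4.4 is the optimistic end.

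Importance is modest. This is one secondary endpoint, its test is nearly valid, and the primary analysis of the continuous SANDE score is unaffected. It is a worthwhile improvement that the plan could do without.

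**What to change.** Keep the item 9 covariates as planned. Fit every item 9 model, including the missing-as-non-responder sensitivity analysis, by Firth's penalised likelihood with profile-likelihood intervals. In PROC LOGISTIC this is FIRTH with CLODDS=PL on the MODEL statement. State in the SAP that significance is judged by whether that interval excludes 1.

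Optionally, add the difference in responder proportions with a 95% interval beside each odds ratio. Tables 14.2.10.1 to 14.2.10.3 already plan the proportions. The same Firth option could serve item 10 if an odds ratio is reported there; no bias was calculated for that item.

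The cost is one SAS option and one or two SAP sentences, with no new data. Reported odds ratios will lie closer to 1 and power falls by about 2 to 4 points: 20-26% against 23-29% at OR 2, 47-54% against 50-58% at OR 3, and 73-78% against 76-81% at OR 4.4. Part of that gap is the planned test's slightly higher level: at OR 1 it rejected 0.4 to 1.3 points more often than Firth.

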3.3.4. Missing Data and Outliers

Every effort will be made to obtain required data at each scheduled evaluation from all subjects. See section 3.3.5 for details of imputing missing dates. A sensitivity analysis will be performed for the primary endpoint imputing missing data by multiple imputation. See section 5.2.1 for details. Unless otherwise specified, other missing data will not be imputed.

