4.1. MODIFIED INTENT-TO-TREAT (MITT) POPULATION

The modified Intent-to-Treat Population (mITT) will include all randomized subjects who have at least a baseline and one post-baseline SANDE part 1 assessment. This is the primary population for efficacy analyses and subjects will be analyzed based on their randomized treatment

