5.2. EFFICACY ANALYSIS

Analyses of efficacy will be conducted using the Study Eye. For all efficacy analyses by Study Eye, a secondary analysis will be conducted using all qualifying eyes. The primary and secondary efficacy analyses will be performed on the mITT Population and presented by treatment group. The dry eye symptom questionnaires can be viewed in Appendix IV of the protocol.

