10. PROPOSED TABLES, LISTINGS, AND FIGURES

Summary Tables

Accountabili	ty and Baseline Characteristics
14.1.1	Subject Disposition (All Subjects Enrolled)
14.1.2.1	Demographics and Baseline Characteristics (All Subjects Enrolled)
14.1.2.2	Dry Eye Assessments at Screening (All Subjects Enrolled)
14.1.3	Study Drug Exposure (All Subjects Treated)
14.1.4.1	Concomitant Medications for Double-Masked Period by Generic Name and Drug
	Classification (Safety Population)
14.1.4.2	Concomitant Medications for Placebo Run-in Period by Generic Name and Drug
	Classification (Run-in Population)
Efficacy (all a	analyses on mITT population)
14.2.1.1	Summary of SANDE Questionnaire Part 1 Global Symptom Score
14.2.2.1.1	Summary of SPEED Questionnaire Total Symptom Score
14.2.2.2	Summary of SPEED Questionnaire Type of Symptom Experience and When
	Symptoms Occur
14.2.3.1.1	Summary of 7-item Symptom Questionnaire Score – Eye Dryness
14.2.3.2.1	Summary of 7-item Symptom Questionnaire Score – Burning/Stinging
14.2.3.3.1	Summary of 7-item Symptom Questionnaire Score – Photophobia
14.2.3.4.1	Summary of 7-item Symptom Questionnaire Score – Foreign Body Sensation
14.2.3.5.1	Summary of 7-item Symptom Questionnaire Score – Blurred Vision
14.2.3.6.1	Summary of 7-item Symptom Questionnaire Score – Itching
14.2.3.7.1	Summary of 7-item Symptom Questionnaire Score – Pain
14.2.4.1.1	Summary of Staining of the Lid Wiper Area – Study Eye
14.2.4.2	Summary of Staining of the Lid Wiper Area – All Qualifying Eyes
14.2.4.3	Summary of Fluorescein Score – Study Eye
14.2.4.4	Summary of Fluorescein Score – All Qualifying Eyes
14.2.4.5	Summary of Lissamine Score – Study Eye
14.2.4.6	Summary of Lissamine Score – All Qualifying Eyes
14.2.5.1.1	Summary of Bulbar Conjunctival Staining Total Score – Study Eye
14.2.5.2	Summary of Bulbar Conjunctival Staining Total Score – All Qualifying Eyes
14.2.5.3	Summary of Bulbar Conjunctival Inferior Nasal Region Score – Study Eye
14.2.5.4	Summary of Bulbar Conjunctival Inferior Nasal Region Score - All
	Qualifying Eyes
14.2.6.1.1	Summary of Corneal Staining Total Score – Study Eye
14.2.6.2	Summary of Corneal Staining Total Score – All Qualifying Eyes
14.2.6.3	Summary of Corneal Staining Inferior Region Score – Study Eye
14.2.6.4	Summary of Corneal Staining Inferior Region Score – All Qualifying Eyes
14.2.7.1.1	Summary of Tear Breakup Time (TBUT) – Study Eye
14.2.7.2	Summary of Tear Breakup Time (TBUT) – All Qualifying Eyes

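### The missing-as-non-responder sensitivity analysis for the SANDE responder endpoint runs on the mITT, so it cannot reach subjects who leave with no post-baseline SANDE Part 1

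*SAP*

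**What the plan says.** SAP 5.2.4 item 9 defines a responder as a subject whose SANDE Part 1 global score falls by at least 20% from baseline to Day 29. The endpoint is analysed by logistic regression on treatment, site and baseline. The analysis is repeated for the frequency and severity scores, with a secondary analysis at Day 15. Item 9 then adds: "A Sensitivity analysis will be performed where all subjects with missing data will be considered non-responders". It names no population of its own.

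The population is set elsewhere:

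- SAP 5.2: "The primary and secondary efficacy analyses will be performed on the mITT Population and presented by treatment group".
- SAP 4.1: the mITT "will include all randomized subjects who have at least a baseline and one post-baseline SANDE part 1 assessment".
- SAP 10 heads the efficacy tables with "analyses on mITT population".
- Protocol 11.4.3, on the responder model: "The model will include all subjects in the mITT population".

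On missing data generally, SAP 3.3.4 says: "Unless otherwise specified, other missing data will not be imputed". The one dropout figure in the plan is in SAP 3.1, repeated from Protocol 11.2: "Assuming a dropout rate prior to Visit 3 of 10%, this provides approximately 60 subjects with post-baseline data".

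**The concern.** Counting missing subjects as non-responders is meant to test whether a responder difference survives when withdrawals are treated as failures. Here the population rule acts before the missing-data rule. A subject without any post-baseline SANDE Part 1 is removed from the mITT, so there is no missing value left to reclassify. The withdrawals that the plan budgets for, those before Visit 3, are largely the ones that the analysis cannot see.

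At stake is the reading of a secondary endpoint. If early withdrawals fall unevenly across arms and few subjects are lost later, the sensitivity analysis will nearly reproduce the main result. It would then look like confirmation without having tested the losses that could change the answer.

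**Working it through.** **Size of the excluded group.** SAP 3.2 says that "approximately 65 subjects will be randomly assigned in a 1:1 allocation ratio". The plan's own figure is 65 × (1 − 0.10) = 58.5, given as about 60, so it reproduces to within two subjects. The excluded group is 65 × 0.10 = 6.5, or 65 − 60 = 5, hence about 5 to 7 subjects. Protocol 6.5 says that withdrawals are not replaced. The plan gives no dropout rate between Visits 3 and 4, and no response rate or power for the responder endpoint.

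**Whom the sensitivity analysis can reclassify.** The scheduled post-baseline SANDE Part 1 scores are at Visits 3 and 4.

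- Day 15: an mITT subject without a Day 15 result must have qualified through a later score, so mainly someone who missed Visit 3 and attended Visit 4. That will be very few.
- Day 29: mITT subjects without a Visit 4 score, mainly those lost between Visits 3 and 4.
- A subject who left before Visit 3 with no score: not reached at either visit.

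**Illustration.** These inputs are assumed: 33 active and 32 placebo randomized, six early withdrawals (dA active, dP placebo), no later losses, and response rates of 60% and 40% among those who stay.

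- mITT odds ratio = (0.60/0.40) ÷ (0.40/0.60) = 2.25, a difference of 20 points. With no later losses, the planned sensitivity analysis gives the same.
- On all randomized subjects, the responder rates are 0.60 × (33 − dA)/33 and 0.40 × (32 − dP)/32.

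| Split dA/dP | Active | Placebo | Difference (points) | OR |
|---|---|---|---|---|
| 3/3 | 18.0/33 = 54.5% | 11.6/32 = 36.3% | 18 | 2.11 |
| 5/1 | 16.8/33 = 50.9% | 12.4/32 = 38.8% | 12 | 1.64 |
| 6/0 | 16.2/33 = 49.1% | 12.8/32 = 40.0% | 9 | 1.45 |
| 1/5 | 19.2/33 = 58.2% | 10.8/32 = 33.8% | 24 | 2.73 |

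**The same check in whole subjects.** This assumes rates of about 65% and 35% and uses an unadjusted Wald test of the log odds ratio.

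- 3/3: 20/30 vs 10/29 (OR 3.80, p = 0.015) becomes 20/33 vs 10/32 (OR 3.38, p = 0.019).
- 5/1: 18/28 vs 11/31 (OR 3.27, p = 0.029) becomes 18/33 vs 11/32 (OR 2.29, p = 0.105).
- 1/5: 21/32 vs 9/27 (OR 3.82, p = 0.015) becomes 21/33 vs 9/32 (OR 4.47, p = 0.005).

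**How likely a lopsided split is.** If withdrawal is unrelated to arm, the chance that all six come from the active arm is C(33,6)/C(65,6) = 1.3%. The chance of 5/1 or worse against active is 1.3% + C(33,5) × 32/C(65,6) = 1.3% + 9.2% = 10.5%.

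**Feasibility.** Protocol 6.3, criterion 2, requires SANDE Part 1 frequency and severity scores at Visit 2 before randomization, and randomization is stratified by site. Baseline and site therefore exist for every randomized subject, and the item 9 model can be fitted to all of them.

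**The case against.** Several points on the other side stand and limit the concern.

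- **A reader might infer that the excluded subjects are the likeliest treatment failures.** The documents do not say so. Protocol 6.5 allows withdrawal for any reason and does not list lack of efficacy among its examples. All that can be said is that these subjects are not counted.
- **A reader might infer that early leavers can never be counted.** The documents conflict here. Protocol 9.1 has symptoms assessed at Early Termination. The Early Termination procedures in Protocol 7.9 and the schedules in Protocol Appendix I and SAP 1.2 include no questionnaire at that visit. If Protocol 9.1 is followed, an early leaver with an Early Termination score could enter the mITT, have no nominal Day 15 or Day 29 result, and be counted as a non-responder. Leavers without that score would still be excluded.
- **A reader might infer that the SAP breaches Protocol 11.4.3**, because under the default of no imputation the main model drops mITT subjects with no Day 29 score. The same protocol paragraph leaves missing data from withdrawals and missed assessments to the SAP, and the SAP supplies a rule. Making non-responder imputation the main model would be a preference, not a correction.
- **All-randomized non-responder imputation is itself an assumption.** It scores every withdrawal as a failure, and in the 1/5 case it enlarges the apparent benefit.
- **Much of the information is reported anyway.** SAP 5.1 gives discontinuation reasons by arm, and Listings 16.2.1.1 and 16.2.3 cover study completion and population membership. A reader could redo an unadjusted count by hand.

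None of this removes the central gap: no planned responder analysis covers all randomized subjects.

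**Conclusion.** The concern holds in a limited form. Item 9's sensitivity analysis is confined to the mITT and cannot reach subjects with no post-baseline SANDE Part 1, about 5 to 7 of 65 if the planned dropout occurs and no Early Termination score is collected. It is not empty, since it does reclassify mITT subjects without a Visit 4 score, but at Day 15 it has very little to act on.

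The documents do not support the stronger reading that the responder result is biased in favour of the drug. The direction depends on how early withdrawals split by arm, which is unknown. Balanced losses barely matter (OR 2.25 to 2.11), while a 5/1 or 1/5 split moves it to 1.64 or 2.73. These values rest on the assumed response rates and on no later losses. The endpoint is secondary, in a Phase 2b trial without multiplicity adjustment (SAP 3.3.3), and the primary analysis and sample size are unaffected. This is a cheap improvement to a sensitivity analysis, not a flaw in the trial's main conclusion.

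**What to change.** 1. In SAP 5.2.4 item 9, run the missing-as-non-responder sensitivity analysis on all randomized subjects by assigned arm, at Day 15 and Day 29, for the global, frequency and severity scores. State this as an exception to SAP 5.2 and to the SAP 10 table heading.
2. Leave the main responder model as the SAP has it.
3. Report the number of randomized subjects excluded from the mITT, by arm and with reasons.
4. Reconcile Protocol 9.1 with Protocol 7.9 and both schedules on symptom questionnaires at Early Termination, since this decides who enters the mITT.

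The cost is SAP wording and one population flag; items 1 to 3 need no new data. The downside is slightly lower responder rates in the sensitivity analysis. It treats every withdrawal as a failure and is not always conservative, so it should be read alongside the exclusion counts by arm.
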